## Scientific Background

Approximately 795,000 Americans sustain a stroke each year, placing these individuals at risk for recurrent stroke. One goal of post-acute rehabilitation and medical management of stroke is to reduce the risk for recurrent strokes. Reducing the risk for recurrent stroke is routinely approached by promoting health behaviors that mitigate specific risk factors for stroke. Specific health behaviors that are important for managing these risk factors include adherence to medication routines, smoking cessation, and physical activity.

Physical inactivity throughout the day can lead to cardiovascular risk factors for recurrent stroke. Prolonged time spent physically inactive, or sedentary, has been identified as a distinct risk factor for poor metabolic control, weight management, and all-cause mortality among adults, after controlling for time spent engaged in exercise. Sedentary time that is accumulated in prolong bouts with few sedentary breaks is associated with risks to cardio-metabolic health. Modifying sedentary behavior patterns after stroke may, therefore, modify cardio-metabolic risk factors for recurrent stroke. Promoting participation in daily life activities frequently requires individuals to move out of a seated or reclined position and may support the modification of sedentary behavior patterns after stroke.

Subtle impairments in cognitive functions are common after stroke. These impairments can lead to difficulty monitoring one's behavior to overcome barriers (e.g. balance impairments), and achieve participation-related goals after stroke. Difficulty monitoring and adjusting behavior, may lead to abandonment of daily life activities that require a high level of physical function (e.g. shopping at the grocery store) rather than identifying alternative strategies to return to participation in that activity (e.g. pushing the cart and planning short trips to the grocery store). When daily life activities are abandoned, they may be replaced with sedentary behavior (e.g. watching television at home while a caregiver shops for groceries).

Behavioral activation is an intervention approach that provides explicit structure for self-monitoring behavior. Behavioral activation approaches have been applied among clients with depression, dementia, brain injury, and stroke. Improvements in mood and cognitive functions and reduction in disability have been associated with behavioral activation interventions. We designed an intervention based in behavioral activation to provide explicit structure for monitoring and adjusting behavior to achieve participation in daily life activities that may break up sedentary time after stroke. Our intervention, the Activating Behavior for Lasting Engagement (ABLE) intervention, applies activity scheduling and monitoring and collaborative problem solving to client-selected goals. The ABLE intervention holds promise to promote participation in daily life activities at scheduled times throughout the day to break up long bouts of sedentary time.

## Study Objectives

The purpose of this research study is to assess the feasibility and estimate the effects of a behavioral intervention (the Activating Behavior for Lasting Engagement intervention, ABLE) on sedentary behavior after stroke.

Research Question: What are the effects (sedentary behavior, participation levels) of the ABLE intervention in the chronic stroke population at post-intervention (week 10) and follow-up (week 18)?

HYPOTHESIS A: The ABLE intervention will be associated with less sedentary time accumulated in prolonged bouts over time (ActivPAL).

HYPOTHESIS B: The ABLE intervention will be associated with a greater number of sedentary breaks over time (ActivPAL).

HYPOTHESIS D: The ABLE intervention will be associated with greater participation over time (Stroke Impact Scale-Participation Subscale).

## **Study Design & Methods**

The study is a single-group quasi-experimental study that will estimate within-group effects of the ABLE intervention on sedentary behavior. All assessment at intervention procedures will be completed by trained research staff (research assistants, interventionists) with supervision provided by the principal investigator.

### **Screening Procedures:**

Participants who verbalize interest in the ABLE study over the telephone will be asked to answer questions over the phone regarding their medical history, age, mobility, daily activities (Sedentary Behavior Questionnaire), and location of residence. These questions will determine initial eligibility.

If, based on telephone screening, participants are eligible and continue to indicate interest, an in-person session will be scheduled to review the full informed consent. This session will be completed in the participant's home. After participants have completed the informed consent process, we will complete standardized clinical assessments (PRIME-MD/MINI, Patient Health Questionnaire-9) to determine eligibility. Participants will complete the PRIME-MD/MINI and Patient Health Questionnaire-9 to screen for mood. These are valid and reliable screening measures (Gilbody et al., 2007; Kroenke, et al., 2002; Spitzer et al., 1999).

### **Baseline Assessment Procedures:**

Participants who provide informed consent, complete screening procedures, and are found to be eligible based on our eligibility criteria will then complete Baseline 1.

#### *BASELINE 1 ASSESSMENTS*

Demographic (age, gender, race, ethnicity, education, vocation, pre-stroke residential status and social support), medical (stroke etiology and date of onset, co-morbidities, medications), and rehabilitation history (type and duration) will be gathered via participant interview and medical record review.

Self-Administered Comorbidity Questionnaire is a participant-reported measure of comorbidities. Participants are asked to report on the presence or absence of specific chronic diseases, if they receive treatment for the disease, and if the disease interferes with their daily life activities.

The Stroke Impact Scale-Participation Subscale is a valid and reliable measure of self-reported engagement in community activities. Participants are asked to rate the degree to which they feel restricted in 10 types of participation on a 1 to 5 Likert-type scale. Scores are summed and converted to a 0 to 100 scale where 100 indicates no participation restrictions.

ActivPAL(TM) monitors will be used to assess sedentary behavior and step count over 7 days. The ActivPAL is a small, lightweight monitor that quantifies time spent in sitting, reclined, standing, and stepping. The participant will be provided the "ActivPAL Guide" as a reference guide. We will follow a 24-hour wear protocol in which the participants will wear the device on their thigh for 7 days. During the BASELINE 1 assessment session, the researcher will train the participant on appropriate care and use of the device. The ActivPAL will be waterproofed and fastened to the individual's thigh using a non-latex, gentle adhesive (Tegaderm). Participants will also be asked to record their bedtime and waking time in the "ActivPAL Diary". Sedentary bouts, sedentary breaks, and steps per day will be assessed using the ActivPAL monitor.

#### *BASELINE 2 ASSESSMENTS*

BASELINE 2 assessments will be conducted after a 4-week delay. Due to the nature of our 7-day ActivPAL(TM) monitoring, BASELINE 1 occurs during week 1 of the study. The 4-week delay is a time period that we dose-matched to the intervention period, in which there is no intervention and no activity monitoring occurs. This occurs during weeks 2-5 of the study. BASELINE 2 assessments described below will occur during week 6 of the study.

Questionnaires will be asked over the telephone, and a researcher will meet the participant at their home to initiate one week of ActivPAL(TM) monitoring as described below. (Estimated participant time: 60 minutes)

ActivPAL(TM) monitors will be used to assess sedentary behavior and step count over 7 days. Participants will be provided with the "ActivPAL Guide" as a reference guide. The ActivPAL is a small, lightweight monitor that quantifies time spent in sitting, reclined, standing, and stepping. We will follow a 24-hour wear protocol in which the participants will wear the device on their thigh for 7 days. During the BASELINE 2 assessment session, the researcher will train the participant on appropriate care and use of the device. The ActivPAL will be waterproofed and fastened to the individual's thigh using a non-latex, gentle adhesive (Tegaderm). Participants will also be asked to record their bedtime and waking time in the "ActivPAL Diary." Sedentary bouts, sedentary breaks, and steps per day will be assessed using the ActivPAL monitor.

The Stroke Impact Scale-Participation Subscale is a valid and reliable measure of self-reported engagement in community activities. Participants are asked to rate the degree to which they feel restricted in 10 types of participation on a 1 to 5 Likert-type scale. Scores are summed and converted to a 0 to 100 scale where 100 indicates no participation restrictions.

#### **ABLE Intervention Procedures**

Once participants have completed baseline testing procedures, they will participate in up to 12 intervention sessions. These sessions will be delivered by a rehabilitation professional who has experience in stroke rehabilitation. Each intervention session will last approximately 45 minutes.

The sessions will occur at the participant's home or at a participant-preferred location in the community.

**ABLE INTERVENTION:** Intervention sessions may be video recorded. During the first intervention session, the participant will describe a typical weekday, Saturday, and Sunday through a semi-structured interview and the "Intervention: Daily Schedule Worksheet." During this process, the therapist will ask the participant to identify portions of the day in which they spend prolonged amounts of time in a seated position. Participants will be oriented to the importance of breaking up sitting time into shortened bouts throughout the day using participation in meaningful daily life activities. Participants will then complete the Activity Card Sort to identify meaningful daily life activities that could be incorporated throughout the day and week to break up prolonged sedentary time. These activities will be documented in the participant's workbook.

Subsequent intervention sessions will focus on scheduling and monitoring participation in daily life activities during times of the day or during activities in which prolonged bouts of sitting time were identified. The sessions will focus around specific time periods that were identified (e.g. every day after lunch, the participant spends 3 hours seated in the recliner) or specific activities in which the participant identifies prolonged sitting time (e.g. while watching television). The participant will select an activity and the therapist will collaborate with the participant to identify strategies for using this activity to break up prolonged seated time. The participant will use a worksheet to schedule the activities and develop a plan for self-monitoring. During the following intervention sessions, the therapist and participant will review the planned schedule and identify successes and barriers to these activities. The participant and therapist will collaboratively generate solutions to identified barriers and a revised plan will be established.

The intervention therapist will document intervention sessions on the "Intervention: Session Notes" document.

After completion of 12 intervention sessions, participants will complete post-intervention assessments and activity monitoring.

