### **Post-Intervention Assessment Procedures**

ActivPAL(TM) monitors will be used to assess sedentary behavior and step count over 7 days. Participants will be provided with the "ActivPAL Guide" as a reference guide. The ActivPAL is a small, lightweight monitor that quantifies time spent in sitting, reclined, standing, and stepping. We will follow a 24-hour wear protocol in which the participants will wear the device on their thigh for 7 days. During the BASELINE 2 assessment session, the researcher will train the participant on appropriate care and use of the device. The ActivPAL will be waterproofed and fastened to the individual's thigh using a non-latex, gentle adhesive (Tegaderm). Participants will also be asked to record their bedtime and waking time in the "ActivPAL Diary." Sedentary bouts, sedentary breaks, and steps per day will be assessed using the ActivPAL monitor.

*The following questionnaire will be conducted via the telephone:*

The Stroke Impact Scale-Participation Subscale is a valid and reliable measure of self-reported

engagement in community activities. Participants are asked to rate the degree to which they feel restricted in 10 types of participation on a 1 to 5 Likert-type scale. Scores are summed and converted to a 0 to 100 scale where 100 indicates no participation restrictions.

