## **Statistical Considerations**

**Primary Outcome Measures:**

1. Change in daily sedentary time accumulated in bouts greater than or equal to 30 minutes (Baseline to Week 11), ActivPAL
2. Change in daily number of sedentary breaks (Baseline to Week 11), ActivPAL

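### Post-intervention assessment is tied to completing 12 sessions in one place and to week 11 in another, with no rule for participants who attend fewer sessions or finish late

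*Combined protocol and SAP*

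**What the plan says.** ABLE Intervention Procedures gives the number of sessions as a ceiling: "they will participate in up to 12 intervention sessions". The closing sentence of that section makes the assessment follow a full course: "After completion of 12 intervention sessions, participants will complete post-intervention assessments and activity monitoring". The next section, headed "Post-Intervention Assessment Procedures", describes the monitor and the telephone questionnaire but names no study week.

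The second baseline is handled differently, because it has a week: "BASELINE 2 assessments described below will occur during week 6 of the study". The length of the intervention is given only indirectly: "The 4-week delay is a time period that we dose-matched to the intervention period".

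Statistical Considerations uses the calendar. Both primary outcomes run from baseline to week 11, for example "Change in daily number of sedentary breaks (Baseline to Week 11), ActivPAL". Primary and Exploratory Outcomes labels post-intervention as week 11 and follow-up as week 18, and reports the group's average change with its SD. Study Objectives labels post-intervention as week 10.

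The only text on missing data, under Preliminary Data Screening, is a plan to look at its patterns and at the characteristics of those affected. No section gives a session frequency, a visit window or a rule for a participant who attends fewer than 12 sessions or finishes late.

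**The concern.** The plan permits fewer than 12 sessions, yet the only trigger it states for the post-intervention assessment is completion of 12. The analysis fixes the same assessment at week 11. For someone who stops at eight sessions, for instance, staff following the procedures could conclude that no assessment is due, while an analyst following the statistical section would expect a week-11 value. For someone who finishes late, the two conditions point to different dates.

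This matters because of the design, a "single-group quasi-experimental study that will estimate within-group effects of the ABLE intervention on sedentary behavior". There is no comparison arm, and the reported result is the average within-person change, so the set of people assessed at week 11 determines the estimate. If early stoppers who would still wear the monitor are not asked to, the mean describes people who completed the course rather than people who started it. A week-11 recording that was not made cannot be obtained later.

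**Working it through.** The plan states no figure on this point to reproduce. The check is a comparison of sections plus calendar arithmetic.

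**Calendar implied by the documents**
- Week 1: first baseline. Weeks 2–5: four-week delay. Week 6: second baseline (Baseline 2 Assessments).
- The intervention matches the four-week delay, so it occupies weeks 7–10.
- Post-intervention assessment: week 11 (Statistical Considerations).
- Follow-up: eight weeks after the intervention (Follow-Up Assessment Procedures), 10 + 8 = week 18, which agrees with the stated week 18.

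**Pace at which the statements agree**
- 12 sessions / 4 weeks = 3 per week. At that pace, session 12 falls by the end of week 10 and all statements fit.

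**Other paces (assumed, since none is stated)**
- End of sessions = week 6 + 12 / (sessions per week); assessment in the following week.
- 2 per week: 6 + 6 = week 12, assessment in week 13, two weeks after the primary time point.
- 1 per week: 6 + 12 = week 18, assessment in week 19, after the week-18 follow-up.

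These show only that the session condition and the week can separate. They do not predict the study's actual pace.

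**Fewer than 12 sessions**
- Session rule: a lower number is allowed.
- Assessment trigger, read literally: never met.
- Outcome definition: a week-11 value is needed.
- Change-score text: no session-count restriction, but no statement of what happens when the week-11 value is absent.

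**What a bias would depend on**
- Let f be the share of assessable starters with fewer than 12 sessions, Mc the mean change in completers and Mn the mean change in the others.
- Mean over all assessable starters = (1 − f)Mc + f·Mn.
- Completer mean minus that mean = f(Mc − Mn).
- The documents give neither f nor Mc − Mn. If f is assumed to be 0.10 or 0.20, the completer mean is off by 10% or 20% of the gap, in either direction, and by nothing if there is no gap. People who withdraw from assessment are outside f, because no wording recovers their data.

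**The case against.** The strongest reply is that the sentence on completing 12 sessions is a transition describing the planned course. It does not say that assessment happens only after 12. The rest of the calendar is coherent and favours a fixed visit: the second baseline in week 6, a four-week intervention, both primary outcomes at week 11, and follow-up at week 18. The change-score text carries no completer restriction. This stands, and a fixed week-11 visit may well be what the sponsor intends.

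A reader might go further and infer that the plan excludes non-completers from the analysis. It does not: no section says so.

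A reader might also infer that the study could never detect the problem. That is too strong. Two baselines precede any session, and attendance is recorded ("The intervention therapist will document intervention sessions on the" session-notes form). The missing-data review would describe who is absent, and the week-18 follow-up carries no session condition. Together these would show who is missing and how they differed at the start. They would not supply the week-11 change.

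Finally, assessing everyone at week 11 is a choice with a cost: someone still attending would be measured before the last session. That is a fair point, and it is why the handling of late finishers is left to the sponsor.

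What the reply does not remove is that no sentence gives the week precedence over the session condition, so field staff and the analyst could each follow the text and act differently.

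**Conclusion.** The point holds as an unresolved conflict between a stated trigger and a stated time point. For participants with fewer or late sessions, the session rule, the assessment trigger and the week-11 definition cannot all be followed. Under the literal reading, early stoppers have no primary change score and the reported mean describes completers.

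It would be tempting to conclude that the primary result will be biased, or biased favourably. The documents do not support that: they give no attendance rate, no pace and no difference between completers and others, so neither the occurrence nor the size or direction of a bias can be derived. Permitting fewer than 12 sessions is not an error in itself.

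The conclusion rests on two assumptions: that the intervention lasts four weeks, which is only implied, and that some participants may attend fewer than 12 sessions, which the plan allows. Severity is minor to moderate. This is a single-group study meant to assess feasibility and estimate effects, with no hypothesis test specified. The separate week-10 label in Study Objectives is a discrepancy to correct and adds no weight to the completer argument.

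**What to change.** 1. Reconcile the two statements on the number of sessions in ABLE Intervention Procedures. No number is proposed here.
2. At the end of that section and in Post-Intervention Assessment Procedures, state that every participant who starts ABLE and has not withdrawn from assessment completes the post-intervention assessment at week 11, even if fewer than 12 sessions were attended.
3. In Primary and Exploratory Outcomes, state that all such assessments enter the change scores.
4. Have the sponsor set the visit window around week 11 and state how participants still attending sessions at that point are handled.
5. Report the number of sessions attended and the actual assessment dates.
6. Align the week-10 label in Study Objectives with week 11.

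The cost is mostly wording. Sessions are already documented, so reporting attendance needs no new data collection. A few extra home visits and telephone questionnaires may be needed for early stoppers, and the estimate may be less favourable than a completers-only mean. If week 11 is also kept for slower attenders, some will be measured before their last session; reporting attendance makes that visible but does not remove it.

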### **Post-Intervention Assessment Procedures**

ActivPAL(TM) monitors will be used to assess sedentary behavior and step count over 7 days. Participants will be provided with the "ActivPAL Guide" as a reference guide. The ActivPAL is a small, lightweight monitor that quantifies time spent in sitting, reclined, standing, and stepping. We will follow a 24-hour wear protocol in which the participants will wear the device on their thigh for 7 days. During the BASELINE 2 assessment session, the researcher will train the participant on appropriate care and use of the device. The ActivPAL will be waterproofed and fastened to the individual's thigh using a non-latex, gentle adhesive (Tegaderm). Participants will also be asked to record their bedtime and waking time in the "ActivPAL Diary." Sedentary bouts, sedentary breaks, and steps per day will be assessed using the ActivPAL monitor.

*The following questionnaire will be conducted via the telephone:*

The Stroke Impact Scale-Participation Subscale is a valid and reliable measure of self-reported

engagement in community activities. Participants are asked to rate the degree to which they feel restricted in 10 types of participation on a 1 to 5 Likert-type scale. Scores are summed and converted to a 0 to 100 scale where 100 indicates no participation restrictions.

### **Follow-Up Assessment Procedures (8 weeks post-intervention)**

ActivPAL(TM) monitors will be used to assess sedentary behavior and step count over 7 days. Participants will be provided with the "ActivPAL Guide" as a reference. The ActivPAL is a small, lightweight monitor that quantifies time spent in sitting, reclined, standing, and stepping. We will follow a 24-hour wear protocol in which the participants will wear the device on their thigh for 7 days. During the BASELINE 1 assessment session, the researcher will train the participant on appropriate care and use of the device. The ActivPAL will be waterproofed and fastened to the individual's thigh using a non-latex, gentle adhesive (Tegaderm). Participants will also be asked to record their bedtime and waking time in the "ActivPAL Diary." Sedentary bouts, sedentary breaks, and steps per day will be assessed using the ActivPAL monitor.

*The following questionnaire will be conducted via the telephone:*

The Stroke Impact Scale-Participation Subscale is a valid and reliable measure of self-reported engagement in community activities. Participants are asked to rate the degree to which they feel restricted in 10 types of participation on a 1 to 5 Likert-type scale. Scores are summed and converted to a 0 to 100 scale where 100 indicates no participation restrictions.

